6.2.3. Safety Endpoints

The safety and tolerability of ALXN1210 will be evaluated from baseline to Week 26 and throughout the extension period by physical examinations, vital signs, physical growth (height,

weight, and head circumference [the latter only in patients who are ≤ 3 years of age]), electrocardiograms (ECGs), laboratory assessments, and incidence of AEs and serious adverse events (SAEs). The proportion of patients who develop antidrug antibodies (ADAs) will also be assessed.

7. INVESTIGATIONAL PLAN

7.1. Summary of Study Design

This is a Phase 3, open-label, single-arm multicenter study to evaluate the PK/PD, safety, and efficacy of ALXN1210 administered by intravenous (IV) infusion to pediatric patients (< 18 years of age) with PNH. The study consists of a 4-week Screening Period, a 26-week Primary Evaluation Period, and an Extension Period.

Consenting patients will be screened for study eligibility up to 4 weeks prior to Day 1. Patients who satisfy all of the inclusion criteria and all of the exclusion criteria will be enrolled into the Primary Evaluation Period and receive a weight-based loading dose of ALXN1210 on Day 1, followed by weight-based maintenance treatment with ALXN1210 on Day 15 and once every 8 weeks (q8w) thereafter for patients weighing \geq 20 kg, or once every 4 weeks (q4w) for patients weighing \leq 20 kg, for a total of 26 weeks of treatment. For patients entering the study on eculizumab therapy, Day 1 of study treatment will occur 2 weeks from the patient's last dose of eculizumab.

An interim analysis of data, including ALXN1210 PK and free C5 levels, will be conducted after 4 patients weighing \geq 5 kg to < 40 kg have completed dosing through Day 71. Enrollment of patients will proceed without interruption while the analysis is ongoing. The accrued safety and PK/PD data will be assessed to ensure that ALXN1210 treatment is well tolerated and is providing adequate complement inhibition. Based on this review, the dose regimen may be adjusted. In addition, an independent Data Monitoring Committee (DMC) will review safety data from the study on a regular basis.

After completion of all pre-dose assessments on Day 183, all patients will enter an Extension Period and continue to receive ALXN1210 according to the appropriate weight-based regimen. The Extension Period will continue until the product is registered or approved (in accordance with country-specific regulations) or for up to 4 years, whichever occurs first, except in Norway where the Extension Period will be 4 years. The end of study is defined as the last patient's last visit or follow-up (whether on site or via phone call) in the Extension Period.

7.2. Discussion of Design and Control

This is an uncontrolled, open-label study of ALXN1210 treatment in pediatric patients. Given the ongoing ALXN1210 clinical program in adults with PNH and the data already generated in an eculizumab clinical study in pediatric patients with PNH (M07-005), a single-arm design was deemed appropriate to investigate the PK/PD, efficacy, and safety of ALXN1210 in the pediatric population. The rarity of PNH in the pediatric population precludes feasibility of a trial with a larger sample size. Ten patients should be sufficient to adequately describe PK/PD in this population while enabling study conduct within a reasonable time frame for making this important treatment available to patients, given the challenges of finding these rare pediatric patients and enrolling them into a prospective, interventional study. The proposed sample size is consistent with the principles of extrapolating the PK/PD and safety/efficacy from adults to pediatric patients given that the disease pathogenesis and mechanism of action of the drug are similar between these two population subsets. This study is descriptive in nature and not

statistically powered for hypothesis testing. This approach was discussed in the context of the agreed pediatric investigation plan of ALXN1210 in PNH (EMEA-002077-PIP01-16).

The disease pathophysiology and clinical response to ALXN1210 treatment is expected to be similar between adult and pediatric PNH populations, as demonstrated in the eculizumab clinical development program. Thus, the efficacy parameters in this study of ALXN1210 are modelled on those selected for study in adult patients with PNH.

The safety parameters being evaluated are commonly used in clinical trials per International Conference on Harmonisation (ICH) and good clinical practice (GCP) guidance documents.

Pediatric FACIT-Fatigue questionnaireg		X	X		X		X		X
Physical examination	X								X
Abbreviated physical examinationh		X	X	X	X	X	X	X	
Vital signs ⁱ	X	X	X	X	X	X	X	X	X
Safety 12-Lead ECGi	X				X				X
Chemistry including LDH ^k	X^{l}	X	X	X	X	X	X	X	X
Hematology including free hemoglobin and coagulationk	X	X	X	X	X	X	X	X	X
Urinalysis and urine chemistry ^k	X	X	X		X		X		X
PK/PD sampling ^m		X	X		X		X		X
Immunogenicity (ADA) ⁿ		X			X		X		X
Review safety cardo		X	X	X	X	X	X	X	X
Breakthrough hemolysis ^p					←Monitor continuously	ontinuously→	•		
Concomitant medications	X				←Monitor c	←Monitor continuously→	•		
Adverse events	X				←Monitor continuously	ontinuously→	•		
ALXN1210 administration (patients weighing < 20 kg) ^{q,r}		Xs	X	X	X	X	X	X	
ALXN1210 administration (patients weighing $\geq 20 \text{ kg}$) ^q		X^{s}	X		X		X		
A blance destinance A DA = and during another DOC = algorithmedia	- 100° :	Josephonio	To the second second	$T_{\rm col} = 100$	d of infinite	TT - 2011: 40	A T	OIT Est	

Abbreviations: ADA = antidrug antibody; ECG = electrocardiogram; eCRF = electronic case report form; EOI = end of infusion; ET = early termination; FACIT-Fatigue = Functional Assessment of Chronic Illness Therapy-Fatigue Scale; LDH = lactate dehydrogenase; N/A = not applicable; PD = pharmacodynamics; PK = pharmacokinetics;

PNH = paroxysmal nocturnal hemoglobinuria; RBC = red blood cell; WBC = white blood cell
Note: If a patient discontinues from the study, an ET visit will be performed, and the Sponsor and site monitor should be notified as soon as possible. In addition, a Follow-up

Phone Call will be performed 8 weeks (± 5 days) following the patient's last ALXN1210 dose to collect concomitant medications, procedures, and adverse events.

The primary endpoint assessment is before dosing on Day 183. Dosing on Day 183 is the start of the Extension Period. Please refer to additional Day 183 postdose assessments in Table 2.

Schedule of Study Visits and Assessments: Screening Through End of Primary Evaluation Period (Continued)

- been vaccinated prior to initiating ALXN1210 treatment should receive prophylactic antibiotics prior to and for at least 2 weeks after meningococcal vaccination. Patients who ^b All patients must be vaccinated against meningococcal infections within 3 years prior to, or at the time of, initiating study drug. Patients who initiate study drug treatment less than 2 weeks after receiving a meningococcal vaccine must receive treatment with appropriate prophylactic antibiotics until 2 weeks after vaccination. Patients who have not cannot be vaccinated must receive antibiotic prophylaxis for the entire treatment period and for 8 months following last dose.
 - WBC (granulocyte and monocyte) and RBC clone size measured by high-sensitivity flow cytometry at Screening and Day 1; RBC clone size only on Day 71 and Day 183.
- Height at baseline and Day 183 only; weight is collected predose on dosing days.
- Pregnancy testing is required only for female patients of childbearing potential (ie, have achieved menarche). Serum pregnancy test is performed at Screening and Day 183, urine (or serum if required by site policy) pregnancy test at all other required time points. A negative pregnancy test result is required prior to administering study drug to female patients of childbearing potential at the indicated study visits.
 - Investigator or designee assessment of the following events: fatigue, hemoglobinuria, abdominal pain, dyspnea, dysphagia, chest pain, and erectile dysfunction. On dosing days, assessments will be performed prior to dosing.
- On dosing days, assessments will be performed prior to dosing. Pediatric FACIT-Fatigue only in patients \geq 5 years of age (self-reported by patients who were \geq 8 years of age at the time of enrollment and reported by caregivers for patients who were ≥ 5 to < 8 years of age at the time of enrollment).
 Abbreviated physical examination consists of a body system relevant examination based upon Investigator (or qualified designee) judgment and patient symptoms. At least 1
 - body system must be checked for an abbreviated exam.
- mmHg]), heart rate (beats/minute), respiratory rate (breaths/minute), and temperature (degrees Celsius [°C] or degrees Fahrenheit [°F]). On dosing days, vital signs will be taken Vital sign measurements will be taken after the patient has been resting for at least 5 minutes and will include systolic and diastolic blood pressure (BP) (millimeters of mercury

- For patients entering the study on eculizumab therapy, Day 1 should occur 2 weeks from the patient's last dose of eculizumab.

Schedule of Study Visits and Assessments: Extension Period – Day 183 to Day 911 Table 2:

Period												Ex	Extension Period	ı Perio	-											
Study Day	183ª	211 q4w only	239	267 q4w only	295	323 3 q4w onty	351 3 qq	379 4 q4w only	407 43 44 on	435 46 q4w onty	463 491 q4w only	491 519 q4w only	19 547 q4w only	7 575 w by	603 q4w onty	631	659 q4w only	687	715 q4w only	743	771 q4w onty	799	827 q4w only	855	883 q4w only	911
Window (day)	± 2	SŦ	±5	#	£	£	# 5#	F 57	Ŧ SŦ	Ŧ F F	FF 5F	5 ±5	5 = 25	£	SŦ	Ŧ	SŦ	#	SF	5 ∓	F	5 Ŧ	SŦ	#	£	Ŧ
PNH clone size ^b							X							×												×
Head circumference (patients ≤ 3 years of age)			×		×		×		×	^	×	×	>	×		×		×		X		×		×		×
Height and weight ^c		X	×	X	×	X	×	X	~ X	X	XX	X	X	×	X	×	X	×	X	X	X	X	X	×	X	×
Pregnancy test ^d			×		×		×	. 1	×	X	.,	X		×		×		×		X		X		×		×
PNH symptomatology ^e			×		X		X							X						X						×
Pediatric FACIT-Fatigue questionnaire ^f							×							×						X						×
Abbreviated physical examination ⁸			×		×		×							×						X						×
Vital signs ^h			×		×		×				-			×						X						×
Chemistry including LDH ⁱ			×		×		×							×						X						×
Hematology including free hemoglobin and coagulation			×		×		×							×						X						×
Urinalysis and urine chemistry ⁱ			×		×		×							×						X						×
PK/PD samplingi	X						X							X						X						X
Immunogenicity (ADA) ^k							X							X						X						X
Review safety card	X	X	X	X	X	X	X	X	γ ×	$X \mid X$		X X	X >	Χ .	X	X	X	X	X	X	X	X	X	X	X	X
Breakthrough hemolysis ^m												⊷Mon	←Monitor continuously→	ntinuon	sly→											
Concomitant medications												moM→	←Monitor continuously→	ntinuon	sly→											
Adverse events												⊷Mon	←Monitor continuously→	ıtinuou	sly→											
Record Transfusions												⊷Mon	←Monitor continuously→	ntinuon	sly→											
ALXN1210	X^{a}	X	X	X	X	X	X	X	γ X	X	$X \mid X$	X A	X >	X	X	X	X	X	X	X	X	X	X	X	X	×
administration (patients weighing $< 20 \text{ kg})^{n,o}$																										
ALXN1210	X^{a}		×		X		×		×	ζ	×	X	>	×		X		×		X		X		X		×
administration (patients weighing $\geq 20 \text{ kg})^n$																										
Abbreviations: $\Delta D \Delta = \text{antidm} \alpha \text{ antihody}$. $FCG = \text{electrocard}$	ortidmio	antib	ody. I	اللي	plantr	nogrdi	ooram	. PCB	liouram: oCRE = alactronic case renort form: FOI = and of infusion: FACIT Estima = Functional Assessment of	octron	9000 01	10001	4 form	· FOI	- and	of inf		FACT	T Fatir	= 9114	Finneti	/ lono	100000	nonto	4	

Abbreviations: ADA = antidrug antibody; ECG = electrocardiogram; eCRF = electronic case report form; EOI = end of infusion; FACIT-Fatigue = Functional Assessment of Chronic Illness Therapy-Fatigue Scale; LDH = lactate dehydrogenase; PD = pharmacodynamics; PK = pharmacokinetics; PNH = paroxysmal nocturnal hemoglobinuria; q4w = once every 4 weeks; RBC = red blood cell

Note: A follow-up phone call to collect concomitant medications, procedures, and adverse events is required 8 weeks (\pm 5 days) after the patient's last dose of ALXN1210 in the following circumstances:

Schedule of Study Visits and Assessments: Extension Period – Day 183 to Day 911 (Continued)

- 1. Patient terminates from the study early.
- 2. Patient completes the study on the q4w regimen and does not initiate commercially available PNH treatment within 8 weeks of their last ALXN1210 dose.
 - ^a Extension Period begins at the start of Day 183 dosing.
- ^b Granulocyte and RBC clone size measured by high-sensitivity flow cytometry.
 - ^c Height on Days 575 and 911 only; weight is collected predose.
- d Pregnancy testing is required only for female patients of childbearing potential (ie, have achieved menarche). Serum pregnancy test is performed only if required by site policy. Urine pregnancy testing may be performed by local laboratory. A negative pregnancy test result is required prior to administering study drug to female patients of childbearing potential at the indicated study visits. Additional pregnancy tests (urine or serum) may also be performed at any visit at the Investigator's discretion.
 - Investigator or designee assessment of the following events: fatigue, hemoglobinuria, abdominal pain, dyspnea, dysphagia, chest pain, and erectile dysfunction. On dosing days, assessments will be performed prior to dosing.
- On dosing days, assessments will be performed prior to dosing. Pediatric FACIT-Fatigue only in patients \geq 5 years of age (self-reported by patients who were \geq 8 years of age at the time of enrollment and reported by caregivers for patients who were \geq 5 to < 8 years of age at the time of enrollment).
 - Abbreviated physical examination consists of a body system relevant examination based upon Investigator (or qualified designee) judgment and patient symptoms. At least 1 body system must be checked for an abbreviated exam.
- h Vital sign measurements will be taken after the patient has been resting for at least 5 minutes and will include systolic and diastolic BP (millimeters of mercury [mmHg]), heart rate (beats/minute), respiratory rate (breaths/minute), and temperature (degrees Celsius [°C] or degrees Fahrenheit [°F]). On dosing days, vital signs will be taken predose.
 - Clinical laboratory measurements will be collected predose and not from a heparinized line.
- dose infusion, prior to administration of the dose. End-of-infusion samples will be drawn from the patient's opposite, noninfused arm. All collection times will be recorded in the after the end of infusion) on Days 351, 575, 743, and 911. To minimize needle sticks to the patient, the predose sample may be drawn through the venous access created for the Serum samples for PK/PD analyses will be collected at end-of-infusion (EOI) on Day 183; predose (within 0.5 hours prior to the start of infusion) and at EOI (within 0.5 hours eCRF. In the event that a supplemental dose is administered, predose and EOI blood samples will be collected for PK/PD analysis. In the event of breakthrough hemolysis, a serum sample for PK/PD analysis will be collected.
- Samples for ADA will be collected predose or at any time during the visit when a dose of study drug is not administered.
- Review the Clinical Trial Participant Safety Information Card with the patient and discuss the importance of carrying the safety card at all times, and the risks associated with ALXN1210 treatment, including the risk of meningococcal infection.
- " If a suspected event of breakthrough hemolysis occurs, LDH, PK, and PD parameters will be analyzed at the central laboratory. If the suspected event of breakthrough hemolysis does not occur at a scheduled visit, an unscheduled visit should occur for evaluation of the patient and collection of the required LDH, PK, and PD parameters.
 - Dose regimen is based on body weight obtained at the study visit. If the study drug needs to be prepared the night prior to the visit, the weight from the previous visit may be
- Should a patient's weight change from < 20 kg to \geq 20 kg on a "q4w only" visit, the patient will receive the q4w dose that day; at the patient's next q8w visit, the new q8w dose will be given.

Protocol ALXN1210-PNH-304 Amendment 3 (Global) 22 Apr 2020

Schedule of Study Visits and Assessments: Extension Period - Day 939 to Day 1639 Table 3:

													ļ													
Period													Exten	Extension Period	r10d							,				
Study Day	939 q4w onty	L 96	995 q4w only	1023	1051 q4w only	1079	1107 q4w only	1135	1163 q4w only	1191	1219 q4w only	1247	1275 q4w only	1303	1331 q4w only	1359	1387 1 44w only	1415 1	1443 1 q4w onty	1471	1499 q4w only	1527	1555 q4w only	1583	1611 q4w only	1639 ET/ EOS
Window (day)	£	#	#	ŧ	£	#2	恕	#	£	ŧ	Ħ	ŧ	£	ŧ	£	ŧ	£	th th	H	tt	£	tt.	£	#	th.	#
PNH clone size ^b						X								×												×
Head circumference (patients ≤ 3 years of age)		×		×		×		×		×		×		×		×		×		×		×		×		×
Height and weight ^c	X	X	X	X	X	X	X	×	X	×	X	×	X	×	X	×	X	X	X	×	X	×	X	×	X	×
Pregnancy test ^d		X		X		X		X		X		×		X		×		X		×		×		×		×
PNH symptomatology ^e						X								×						×						×
Pediatric FACIT-Fatigue questionnaire ^f						X								×						×						×
Physical examination																										×
Abbreviated physical examination ^g						X								×						×						
Vital signs ^h						X								×						×						×
Safety 12-Lead ECGi																										×
Chemistry including LDH ^j						X								X						X						X
Hematology including free hemoglobin and coagulation						X								×						X						×
Urinalysis and urine chemistry ^j						X								X						X						X
PK/PD sampling ^k						X								X						X						X
Immunogenicity (ADA) ¹						×								×						×						×
Review safety card ^m	X	X	X	X	X	X	X	X	X	X	X	X	X	X	X	X	X	X	X	X	X	X	X	X	X	X
Breakthrough hemolysis ⁿ												—Mor	-Monitor continuously-	ntinuou	sly→											
Concomitant medications												-Mor	—Monitor continuously→	ntinuou	sly→											
Adverse events												—Mor	—Monitor continuously→	ntinuou	sly→											
Record transfusions												—Mor	←Monitor continuously→	ntinuou	sly→											
ALXN1210 administration (patients weighing < 20 kg ^{lo.p}	X	×	X	×	X	X	X	×	X	×	X	×	X	×	X	×	X	×	X	×	X	×	X	×	X	
ALXN1210 administration (patients weighing $\geq 20 \text{ kg}$)°		X		×		X		×		×		×		×		×		×		×		×		×		
															•	•	•									

Schedule of Study Visits and Assessments: Extension Period – Day 939 to Day 1639 (Continued)

FACIT-Fatigue = Functional Assessment of Chronic Illness Therapy-Fatigue Scale; LDH = lactate dehydrogenase; PD = pharmacodynamics; PK = pharmacokinetics; PNH = Abbreviations: ADA = antidrug antibody; ECG = electrocardiogram; eCRF = electronic case report form; EOI = end-of-infusion; EOS = end of study; ET = early termination; paroxysmal nocturnal hemoglobinuria; q4w = once every 4 weeks; RBC = red blood cell

Note: A follow-up phone call to collect concomitant medications, procedures, and adverse events is required 8 weeks (± 5 days) after the patient's last dose of ALXN1210 in the

- 1. Patient terminates from the study early.
- 2. Patient completes the study on the q4w regimen and does not initiate commercially available PNH treatment within 8 weeks of their last ALXN1210 dose.
 - ^a If a patient withdraws early form the study (eg, to begin treatment with marketed product), an ET visit will be performed.
 - ^b Granulocyte and RBC clone size measured by high-sensitivity flow cytometry.
 - ^c Height on Day 1247 and Day 1639/EOS or ET only; weight is collected predose
- Pregnancy testing is required only for female patients of childbearing potential (ie, have achieved menarche). Urine pregnancy testing may be performed by local laboratory. required prior to administering study drug to female patients of childbearing potential at the indicated study visits. Additional pregnancy tests (urine or serum) may also be Serum pregnancy test is performed at ET or Day 1639/EOS only, unless required by site policy; urine pregnancy test at all other visits. A negative pregnancy test result is performed at any visit at the Investigator's discretion.
- Investigator or designee assessment of the following events: fatigue, hemoglobinuria, abdominal pain, dyspnea, dysphagia, chest pain, and erectile dysfunction. On dosing days, assessments will be performed prior to dosing.
- On dosing days, assessments will be performed prior to dosing. Pediatric FACIT-Fatigue only in patients \geq 5 years of age (self-reported by patients who were \geq 8 years of age at the time of enrollment and reported by caregivers for patients who were ≥ 5 to < 8 years of age at the time of enrollment).
 - Abbreviated physical examination consists of a body system relevant examination based upon Investigator (or qualified designee) judgment and patient symptoms. At least 1 body system must be checked for an abbreviated exam.
- h Vital sign measurements will be taken after the patient has been resting for at least 5 minutes and will include systolic and diastolic BP (millimeters of mercury [mmHg]), heart rate (beats/minute), respiratory rate (breaths/minute), and temperature (degrees Celsius [°C] or degrees Fahrenheit [°F]). On dosing days, vital signs will be taken predose.
- Single 12-lead ECG will be collected on Day 1639/EOS or ET. Patients must be supine for approximately 5 to 10 minutes before ECG collection and remain supine but awake
 - during ECG collection.
- Clinical laboratory measurements will be collected predose and not from a heparinized line.
- created for the dose infusion, prior to administration of the dose. End-of-infusion samples will be drawn from the patient's opposite, noninfused arm. All collection times will be recorded in the eCRF. In the event that a supplemental dose is administered, predose and EOI blood samples will be collected for PK/PD analysis. In the event of breakthrough Days 1079, 1303, and 1471; and at any time on Day 1639/EOS or ET. To minimize needle sticks to the patient, the predose sample may be drawn through the venous access Serum samples for PK/PD analyses will be collected predose (within 0.5 hours prior to the start of infusion) and at end-of-infusion (EOI) (within 0.5 hours after the EOI) on hemolysis, a serum sample for PK/PD analysis will be collected.
 - 1 Samples for ADA will be collected predose or at any time during the visit when a dose of study drug is not administered.
- Review the Clinical Trial Participant Safety Information Card with the patient and discuss the importance of carrying the safety card at all times, and the risks associated with ALXN1210 treatment, including the risk of meningococcal infection.
- If a suspected event of breakthrough hemolysis occurs, LDH, PK, and PD parameters will be analyzed at the central laboratory. If the suspected event of breakthrough hemolysis does not occur at a scheduled visit, an unscheduled visit should occur for evaluation of the patient and collection of the required LDH, PK, and PD parameters.
- Dose regimen is based on body weight obtained at the study visit. If the study drug needs to be prepared the night prior to the visit, the weight from the previous visit may be
- Should a patient's weight change from $< 20 \text{ kg to} \ge 20 \text{ kg on a "q4w only"}$ visit, the patient will receive the q4w dose that day; at the patient's next q8w visit, the new q8w dose

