9.2. Treatments Administered

Patients will receive a loading dose of ALXN1210 on Day 1, followed by maintenance dosing of ALXN1210 on Day 15 and q8w thereafter for patients weighing \geq 20 kg, or q4w for patients weighing \leq 20 kg, as shown in Table 6. With the agreement of the Alexion Medical Monitor, the 600 mg loading dose may be given to patients weighing \geq 5 to \leq 10 kg as 2 separate infusions administered no more than 24 hours apart. Dosages are based on the patient's body weight recorded on the day of dosing or the most recently recorded weight. For patients entering the study on eculizumab therapy, Day 1 of study treatment will occur 2 weeks from the patient's last dose of eculizumab.

Table 6:	Loading and Maintenance Treatment Regimen	IS

Body Weight Range (kg) ^a	Loading Dose (mg)	Maintenance Doses (mg)	Maintenance Dosing Frequency
\geq 5 to < 10	600 ^b	300	q4w
$\geq 10 \text{ to} < 20$	600	600	q4w
\geq 20 to < 30	900	2100	q8w
\geq 30 to < 40	1200	2700	q8w
\geq 40 to < 60	2400	3000	q8w
\geq 60 to < 100	2700	3300	q8w
≥ 100	3000	3600	q8w

Abbreviations: q4w = once every 4 weeks; q8w = once every 8 weeks

With the agreement of the Alexion Medical Monitor, administration of a supplemental dose of ALXN1210 is permitted.

After the Primary Evaluation Period, all patients will roll over into an Extension Period and continue their weight-based maintenance dose of ALXN1210 on Day 183 and q8w thereafter for patients weighing ≥ 20 kg, or q4w for patients weighing ≤ 20 kg, until the product is registered or approved (in accordance with country specific regulation) or for up to 4 years, whichever occurs first, except in Norway where the Extension Period will be 4 years.

The actual time of all dose administrations, including any supplemental dose or dose administered as 2 separate infusions as noted above, will be recorded on the patient's eCRF.

^a Dose regimen will be based on body weight obtained at the study visit. If the study drug needs to be prepared the night prior to the visit, the weight from the previous visit may be used.

b With the agreement of the Alexion Medical Monitor, the 600 mg loading may be given to patients weighing ≥ 5 to < 10 kg as 2 separate infusions administered no more than 24 hours apart.

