9.7. Prior and Concomitant Medications and Nonpharmacologic Procedures

Prior medications (including vitamins and herbal preparations)—including those discussed in the exclusion criteria (Section 8.2) and procedures (any therapeutic intervention, such as surgery/biopsy or physical therapy) the patient takes or undergoes within 28 days prior to the start of Screening until the first dose of study drug—will be recorded on the patient's eCRF. In addition, history of meningococcal vaccination must be collected for the 3 years prior to first dose of study drug and vaccination history for Hib and *S pneumoniae* must be collected from birth.

If patients had been treated with eculizumab, a documented regimen history will be collected. Transfusions of pRBCs received within 1 year prior to first study drug administration will be recorded on the patient's eCRF.

All medication used and procedures undertaken during the study will be recorded in the patient's source document/medical chart and eCRF. This record will include all prescription drugs, herbal products, vitamins, minerals, over-the-counter medications, and current medications for PNH. Concomitant medications and procedures will be recorded from the first infusion of study drug through 56 days after the patient's last dose of study drug. Any changes in concomitant medications also will be recorded in the patient's source document/medical chart and eCRF. Any concomitant medication deemed necessary for the patient's standard of care during the study, or for the treatment of any AE, along with the allowed medications described below may be given

at the discretion of the Investigator. However, it is the responsibility of the Investigator to ensure that details regarding all medications are recorded in full in the patient's source document/medical chart and eCRF.

Concomitant use of anticoagulants is prohibited if not on a stable dose regimen for at least 2 weeks prior to Day 1.

Concomitant use of complement inhibitors other than the study treatment is prohibited.

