11.7.6. Collection and Reporting of Adverse Events

11.7.6.1. All Adverse Events

All AEs (serious and nonserious) will be collected from the signing of the informed consent form (ICF) until 56 days after the last dose of study drug for patients with ET or until 56 days after the last dose of study drug for patients who complete the study. All AEs must be recorded on the eCRF upon the Investigator or his/her staff becoming aware of their occurrence.

Investigators will be instructed to report the SAE including their assessment (eg, severity, seriousness, and potential relatedness to study drug) to Alexion Global Drug Safety (GDS) within 24 hours of first awareness of the event via the Safety Gateway.

If a patient's treatment is discontinued as a result of an AE, study site personnel must clearly capture the circumstances and data leading to any such dose interruption or discontinuation of treatment in the AE and Exposure pages of the eCRF.

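### A q4w completer who starts commercial PNH treatment has no scheduled contact for the second half of the 56-day safety window that the protocol sets

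*Protocol*

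**What the plan says.** **Required window.** Protocol Section 11.7.6.1 sets adverse-event collection "until 56 days after the last dose of study drug for patients with ET" and, for the others, "until 56 days after the last dose of study drug for patients who complete the study". Section 9.7 sets the same limit for other medicines and procedures: "Concomitant medications and procedures will be recorded from the first infusion of study drug through 56 days after the patient's last dose of study drug". Neither section exempts a patient who moves to commercial treatment.

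**Scheduled contact.** The notes to Tables 2 and 3 (Section 7.3) require a call 8 weeks, plus or minus 5 days, after the last dose in two circumstances. The first is early termination. The second is: "Patient completes the study on the q4w regimen and does not initiate commercially available PNH treatment within 8 weeks of their last ALXN1210 dose".

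**Last doses and final visit.** In Table 3 the last q4w dose falls on Day 1611 and the last q8w dose on Day 1583. The final visit is Day 1639, with no dosing.

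**Leaving for marketed product.** Table 3 footnote a gives this as an example of early withdrawal: "eg, to begin treatment with marketed product), an ET visit will be performed". Section 8.3.1 requires the 8-week call for any patient who discontinues from the study. Section 9.2 has the Extension Period run "until the product is registered or approved (in accordance with country specific regulation) or for up to 4 years, whichever occurs first", with a separate rule for Norway.

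**The concern.** The call is the only contact scheduled after the final visit, and for one group the notes remove it without any matching exception in Sections 11.7.6.1 or 9.7. The group is children on q4w who reach Day 1639 and then start commercial treatment within 8 weeks of the last study dose. At Day 1639 such a child is one dosing interval past the last dose, so a start within those 8 weeks is plausible for anyone who continues treatment.

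The exemption is also uneven. Two children may make the same switch; the one who leaves before Day 1639 is called at 8 weeks and the one who completes is not. A wish to stop follow-up once another product has been given cannot explain this, because the early leaver has been given it too.

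At stake is the completeness of post-dose safety data in the lightest children. Section 14.9.1 puts no upper time limit on treatment-emergent events, so an event that nobody asks about is simply absent from the final report. Safety is one of the study objectives (Section 6.1).

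**Working it through.** **Inputs**
- Required window: 56 days after the last dose (Sections 11.7.6.1 and 9.7).
- Last q4w dose: Day 1611. Last q8w dose: Day 1583. Final visit: Day 1639 (Table 3).
- Call: 8 weeks ± 5 days after the last dose (notes to Tables 2 and 3).

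**Check of the calendar**
- 8 weeks = 8 × 7 = 56 days, so the call is aimed at the end of the required window.
- Table 3 visits run every 28 days: 939 + 25 × 28 = 1639, which gives 26 visits.
- q4w dosing from Day 183: (1611 − 183) / 28 = 51 intervals exactly.
- q8w dosing from Day 183: (1583 − 183) / 56 = 25 intervals exactly.

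**Days from last dose to last scheduled contact**

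| Patient | Last scheduled contact | Days after last dose | Part of the 56 days left without a contact |
|---|---|---|---|
| q4w completer, no commercial treatment within 8 weeks | Call | 56 (51 to 61) | None at the nominal day |
| q4w completer, commercial treatment within 8 weeks | Day 1639 visit | 1639 − 1611 = 28 | 56 − 28 = 28 days (28/56 = 50%) |
| q8w completer at Day 1639 | Day 1639 visit | 1639 − 1583 = 56 | None at the nominal day |
| Early termination, including for marketed product | Call | 56 (51 to 61) | None at the nominal day |

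**Effect of visit windows.** The window row of Table 3 is not fully legible in the text, so this step assumes ± 5 days, as Table 2 shows for extension visits after Day 183. With ± 5 days on both the last dose and the final visit:
- q4w: from 1634 − 1616 = 18 days to 1644 − 1606 = 38 days. The stretch without contact is then 56 − 38 = 18 to 56 − 18 = 38 days.
- q8w: from 1634 − 1588 = 46 days to 1644 − 1578 = 66 days.

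Only the second row of the table falls short at nominal days. The q8w result probably explains why the second call circumstance names only the q4w regimen: a q8w completer's final visit already closes the window in person.

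**The case against.** The strongest reply is that no duty has been waived. Section 11.7.6.1 still obliges the site to collect events to 56 days for completers and to record them on becoming aware of them. Section 11.7.6.2 sets no time limit on reporting SAEs thought to be related to study drug, so a serious meningococcal infection judged related stays reportable. To apply the second circumstance at all, the site must also learn whether treatment started within 8 weeks. All of this stands, and it means that what is missing is a scheduled contact, not data capture altogether. It does not supply a prompt to ask about non-serious or unrelated events in days 29 to 56.

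The group is also small. It needs a child still under 20 kg at Day 1611, more than four years after Day 1, in a study of about 13 patients in which children who reach 20 kg move to q8w. The documents do not show that any such child is expected. This too stands, and it sets the severity.

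Four stronger readings are tempting, and the documents do not support them:
- **Completers in general lack cover.** They do not: a q8w patient who reaches Day 1639 has 56 days nominally.
- **q8w patients who leave at approval get no follow-up.** This requires them to be classed as completers, and no section does that. Footnote a and Section 8.3.1 point to early termination and a call. Section 9.2 lets approval end the Extension Period, so the label could be clearer, but that is a matter of terminology.
- **The ± 5 days on the call cuts collection short.** It is an ordinary tolerance, and Section 11.7.6.1 sets the collection period independently of the call date.
- **The SAP's analyses are affected.** The SAP covers only the 26-week report (SAP Section 4), with safety listings up to Day 183 (SAP Section 7.3). Any effect falls on the later final report.

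**Conclusion.** The point holds in a narrow form, as an inconsistency within the protocol. For a q4w completer who starts commercial PNH treatment within 8 weeks, the schedule gives 28 of the required 56 days at nominal visit dates, and days 29 to 56 have no scheduled contact. Under the assumed ± 5 day visit windows, the uncovered stretch is 18 to 38 days. The same switch made before Day 1639 does bring a call.

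This rests on reading the two call circumstances as exhaustive and on the Table 3 dosing days given above. It takes completion to mean reaching Day 1639. The number of children concerned cannot be derived from the documents but is likely to be small. A reader might infer that events in this interval will be lost or need not be collected; neither follows, because the collection duty remains. Severity: minor.

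**What to change.** Reconcile the second call circumstance in the notes to Tables 2 and 3 with Sections 11.7.6.1 and 9.7, by requiring the 8-week call for every q4w completer whether or not commercial treatment has started. Record the start date of commercial treatment, so that events can be shown before and after the switch. For q4w completers who switch, the last scheduled contact then moves from day 28 to day 56 (51 to 61 with the existing tolerance). The note to Table 1 and the rule for q8w completers at Day 1639 need no change.

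As a clarification only, state once whether leaving when the product is approved counts as completion or early termination, so that the call rule applies alike to all such patients. Section 14.5 tabulates completion and withdrawal from the Extension Period separately, so this label is needed in any case.

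The cost is a wording change, one date field and at most a few telephone calls. Some events after the switch will have mixed attribution; the recorded start date lets the report show which they are.
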